5.2 Stratification Factors and Subgroups

The baseline values for the following stratification factors will be summarized using descriptive statistics:

- Prior use of biologics or JAK inhibitors (yes/no)
- Geographic region (North America /rest of world (ROW))

The assigned (IXRS) and actual stratification factors will be summarized and listed for the mis-stratified subjects. In the event which any errors are made in specifying the stratification factors for randomization, all efficacy analyses will be based on the actual classification according to the clinical database.

The following subgroups may be included in the analysis of safety and/or efficacy data.

- BSA involvement (10–20 %, > 20 %)
- PASI (≤ 20 , > 20)
- Baseline modified sPGA score (3, 4, 5)
- Sex (Male, Female)
- Race (White, Non-white)
- Age category (< 40 years, 40–65 years, ≥ 65 years)
- Geographical region (North America, ROW)
- Baseline weight category (<90 kg, ≥ 90 kg)
- Baseline BMI category (<30 kg/m², ≥ 30 kg/ m²)
- Prior use of psoriasis medication (yes, no)
- Prior use of systemic therapies (yes, no)
- Prior use of phototherapies (yes, no) (as collected in MH where MHTERM='Phototherapy' or 'UV light therapy')
- Prior use of biologics (yes, no)
- Prior use of JAK inhibitors (yes, no)
- Prior use of TYK 2 molecules (yes, no)
- Presence of co-morbidities (yes, no; co-morbidities considered include a history of diabetes, cardiovascular diseases, obesity, depression, hypertension, psoriatic arthritis)

5.3 Missing Data

In general, missing data will not be imputed unless specifically stated in this SAP. Refer to [Section 7](#) on handling of missing data for responder analyses.

Handling of Missing Data:

For data collected with start and end dates such as medical history and concomitant medications, the following may be applied to missing or partial dates:

- Start Dates:

- If day is missing, then impute it to be the start of the month (eg, 01MMYYYY); except if the month and year is equal to the first dose date month and year then impute the day to be the same day as the first dose date.
- If month is missing, then impute it to be the start of the year (eg, 01JANYYYY), except if the year is equal to the first dose date year then impute the day and month to be the same as the first dose date.
- If year is missing, then do not impute.
- End Dates:
 - If day is missing, then impute it to be the end of the month (eg, 31MMYYYY), except if the month and year is equal to the last assessment date month and year then the day should be imputed to the last participation date day.
 - If month is missing, then impute it to be the end of the year (eg, 31DECYYYY), except if the year is equal to the last participant date year then the day and month should be imputed to the last participant date day and month.
 - If year is missing, then do not impute.
- For all other type of dates:
 - If only day is missing, then impute it to be the start of the month (eg, 01MMYYYY).
 - If month and day are missing, then impute it to be the start of the year (eg, 01JANYYYY).
 - If year is missing, then do not impute.

5.4 Multiplicity Control

No adjustments for multiplicity control will be performed in this study.

5.5 Data Handling Conventions

[figure not shown]
For safety laboratory data that are continuous in nature the following rules will be applied:

- If a result is less than the lower limit of quantitation (LLOQ), it will be imputed to the value of the lower limit minus 1 significant figure (e.g., if the result of the laboratory test is < 30, a value of 29 will be assigned; if the result of the laboratory test is < 30.0, then a value of 29.9 will be assigned; if the result of the laboratory test is < 1, a value of 0.9 will be assigned; if the results of the lab test is < 0.1, a value of 0.09 will be assigned).
- If a result is above the upper limit of quantitation (ULOQ), it will be imputed to the value of the upper limit plus 1 significant figure.

For PK concentration data, the following rules will be applied:

- For values below the LLOQ, 1/2 LLOQ will be imputed unless otherwise specified.

For values above the ULOQ, ULOQ + 1 unit of significant digit will be imputed unless otherwise specified. The actual reported values will be provided in by-subject listings.

[REDACTED]

[REDACTED]

[REDACTED]

6 SUBJECT DISPOSITION

The number and percentage of subjects who complete and who prematurely discontinue study drug or study, with the reasons for early discontinuation, and the stratification factors as entered in IRT will be summarized by randomized treatment assignment for the ITT Population. The number of subjects who screen-failed with reasons for screen failure will be summarized for all screened subjects. The number of randomized subjects by country and site will be summarized.

6.1 Demographics and Baseline Characteristics

Demographic and baseline characteristics including those defined in [Section 5.2](#) will be summarized descriptively by randomized treatment assignment for the ITT Population.

Body surface area (BSA) will be derived using the Du Bois method.

6.2 Study Drug Exposure and Compliance

The extent of study drug exposure and compliance will be assessed and summarized by actual treatment received for the Safety Analysis Population.

The duration of study drug exposure will be presented in weeks and is defined as last dose date – first dose date + 1 day, regardless of intermittent interruptions. The total dose per subject will be calculated as the sum of all doses for a subject and will be presented for active study drug cohorts only.

Study drug compliance will be based on pill count and is defined as the total number of pills taken divided by the expected number of pills based on the duration of exposure.

Study drug exposure, dosage and compliance will be summarized using descriptive statistics. The frequency and percentage of participants with compliance < 80% and those with compliance > 100% will be summarized by treatment group and overall.

Drug interruptions will be summarized as collected in the Study Drug Administration CRF where any reason for study drug administration stopped other than ‘completed’ will be considered as an interruption. The duration of interruption will be calculated using the start and stop dates entered in this CRF. The number of subjects with drug interruptions and the summary

statistics for the duration of interruption (based on the maximum duration of interruption if more than one interruption per subject) will be presented.

6.3 Protocol Deviations

Prior to database lock, all protocol deviations will be reviewed and confirmed by the Sponsor. Important protocol deviations (IPD) will be identified and summarized by category and listed for the Safety Analysis Population.

International Council for Harmonisation (ICH) E3 guidance defines IPD as a subset of protocol deviations that may significantly impact the completeness, accuracy, and/or reliability of the study data or that may significantly affect a participant's rights, safety, or well-being.

Any IPDs which impact the interpretation of key primary and secondary efficacy analyses and considered for the Per Protocol Population will be identified through the study protocol deviation review process.

The number of subjects that met IPD category of drug compliance below 80% will be programmatically derived based on calculated subject drug compliance as described in [Section 6.2](#).

6.4 Medical History and Concomitant Procedures

Medical history terms and concomitant procedures will be coded using the Medical Dictionary for Regulatory Activities (MedDRA) version 25.0. Frequency of medical history and concomitant procedures will be summarized by treatment group, SOC and PT for the Safety Analysis Population. A by subject listing will also be provided.

6.5 Prior and Concomitant Medications

Prior and concomitant medications will be coded using the Anatomical Therapeutic Chemical (ATC) coding scheme of the World Health Organization Drug Dictionary (WHO DD Global B3 March 2022). All concomitant, prior and prior Psoriasis medications will be summarized by treatment group, ATC2 level and standardized medication name for the Safety Analysis Population. A by-subject listing will also be provided.

Prior medication is defined as medication with an end date prior to the first dose in the study and medication taken at any time during the study (ie, first dose through EOS) is considered concomitant.

Prior psoriasis medications collected on a dedicated CRF will be presented separately and will be classified as phototherapies, biologic therapies, or systemic therapies through manual review by the medical monitor.

7 EFFICACY ANALYSES

All efficacy analyses will be conducted using the mITT Analysis Population. A sensitivity analysis using the ITT or PP analysis set may be performed as appropriate.

The primary and secondary endpoints are based on the efficacy response at the end of treatment (ie. Week 12).

In general, for responder type analyses, the difference in the proportion of subjects between two treatment arms at Week 12 or other timepoints (eg. Week 4, 8, if applicable) and the corresponding two-sided 95% CI will be calculated using the Fisher's exact test or the Chi-squared test depending on the number of observations (if cell counts are less than 5 then use Fisher's). A test of significance for the difference in proportion between two treatment groups will be performed using the Cochran Mantel-Haenszel (CMH) test adjusting for randomization stratification factors and the corresponding two-sided p-value will be presented.

A non-responder imputation will be applied to responder analyses in which subjects who drop out of the study before Week 12 will be considered as a non-responder at the week 12 visit. No imputation will be applied at any other post-baseline visits. [REDACTED]

For continuous efficacy measurements or scores, the treatment difference in the change from baseline between each active treatment and placebo will be compared using an ANCOVA model, with treatment group, visit and randomization stratification factors as fixed effects and baseline measure as a covariate. An unstructured covariance matrix will be used to model the correlation among repeated measurements (if convergence issues are encountered then compound symmetry covariance matrix will be used instead). Within-group least-squares (LS) means, standard errors (SEs), 2-sided 95% CIs, and p-values will be presented for Week 12 and other timepoints, if applicable.

Some efficacy analyses may also be presented by select subgroups of interest such as baseline PASI, age, BMI, race, gender and prior biologic use categories (refer to [Section 5.2](#)). However, given the small sample size, test for statistical significance will not be conducted for subgroup analyses.

[REDACTED]

[REDACTED]

[REDACTED]

[REDACTED]

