10.3.2. Secondary Efficacy Endpoints

Similar analyses as in the primary efficacy analyses will be performed to compare any two active arms.

The proportion of patients in each treatment group and placebo with sPGA categories 0 or 1 (cleared or minimal) at Week 12 will be compared using the Cochran-Mantel-Haenszel test adjusting for stratification factors.

The proportion of patients in each treatment group and placebo with response rate in PASI-50, 90, and 100 at Week 12 relative to baseline will be compared using methods similar to those used for PASI-75.

Change in percent BSA at Week 12 relative to baseline will be performed using ANOVA or analogous nonparametric methods.

Change from baseline in DLQI at Week 12 relative to baseline will be performed using ANOVA or analogous nonparametric methods.

The proportion of patients in each treatment group and placebo with $\geq 75\%$ improvement in PASI Week 12 relative to baseline will be compared using the Cochran-Mantel-Haenszel test adjusting for stratification factors.

No adjustments for multiplicity will be performed.

Graphical methods may be used to display efficacy data.

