7.1 Primary Efficacy Analyses

7.1.1 *Psoriasis Area and Severity Index*

Disease activity will be assessed by the Psoriasis Area and Severity Index (PASI) which derives a score for the severity of psoriatic lesions by evaluating erythema, induration, and scaling in each of 4 body regions, as detailed in [Appendix C](#).

The primary endpoint is the proportion of subjects achieving $\geq 75\%$ reduction in PASI score (PASI-75) at Week 12.

The proportion of subjects achieving PASI-75 will be summarized for each post-dose timepoint by treatment group. The primary efficacy analysis will compare the proportion of subjects achieving PASI-75 at Week 12 between each active treatment and placebo using the CMH method as described in [Section 7](#). This analysis will be repeated at Weeks 4 and 8.

The absolute value, change and percent change from baseline in PASI score will be summarized using descriptive statistics by timepoint and treatment group. Additionally, the difference in the change from baseline between each active treatment and placebo will be assessed using ANCOVA model as described in [Section 7](#). The analysis will be repeated with percent change from baseline as the dependent variable. Estimates of least-squares (LS) means, SEs, 2-sided 95% CIs and p-values will be presented by treatment group for Weeks 4, 8 and 12.

Absolute PASI scores and the proportion of subjects achieving PASI-75, PASI-90, PASI-100, PASI-50 will also be plotted over time by treatment. The proportion of subjects achieving PASI-50, PASI-75, PASI-90 and PASI-100 at Week 12 by treatment will be presented using a bar chart. The percent reduction in PASI at Week 12 for each individual subject will be presented by waterfall plot. Each treatment group will be presented on a separate plot.

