7.2 Secondary Efficacy Analyses

7.2.1 *Psoriasis Area and Severity Index*

To compare the proportion of subjects achieving PASI-75 at 12 weeks among the active treatment groups, the adjusted treatment difference, its associated 95% CI, and two-sided p-value will be presented for all 1:1 treatment comparison using the CMH method.

Time to achievement of each PASI endpoint will also be summarized using descriptive statistics and Kaplan-Meier curves .

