7.4 Physician's Global Assessment

Efficacy will also be assessed by the static Physician's Global Assessment (sPGA) and the scoring system is presented in [Appendix D](#). The frequency and percentage of subjects for each discrete sPGA score (0 through 5) will be summarized by timepoint and treatment group. The proportion of subjects who achieve a sPGA response (defined as sPGA score of "0" ("cleared") or "1" ("minimal")) will be summarized for each post-dose timepoint by treatment group. The adjusted treatment difference in proportion of subjects with a sPGA response of 0 or 1 for each active treatment compared to placebo, its associated 95% CI, and two-sided p-value will be presented for Week 4, 8 and 12 using the CMH method.

Bar charts of the proportion of subjects with the following sPGA scores will be plotted by treatment for each visit: 0, 0/1, 1, 2, 3, 4, 5.

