7.5 Patient-Reported Outcomes

Quality of life (QoL) will be assessed by the following patient-reported outcomes (PRO): the Dermatology Life Quality Index (DLQI), the EQ-5D-5L, and the pruritus numerical rating scale (NRS). The two questions collected in NRS questionnaire will be assessed separated as the average itch within the past 24 hours and the worst itch within the past 24 hours. Since the EQ-5D-5L value sets used to calculate the index score are country-specific and there currently are none available for Czech Republic where some subjects are enrolled in this study, the value set for Poland will be used instead as the closest Eastern European country with available scoring instrument.

DLQI score, NRS average and worst itch scores, and the EQ-5D-5L index score are continuous variables, and the absolute value, change and percent change from baseline in each PRO assessment will be summarized using descriptive statistics by timepoint and treatment group. The absolute value, change and percent from baseline for each PRO measure will be summarized using descriptive statistics by timepoint and treatment group. Additionally, the difference in the change from baseline between each active treatment and placebo will be assessed using ANCOVA model as described in [Section 7](#). The analysis will be repeated with percent change from baseline as the dependent variable. Estimates of least-squares (LS) means, SEs, 2-sided 95% CIs and p-values will be presented by treatment group for Weeks 4, 8 and 12. The absolute value over time will be plotted by treatment for the EQ-5D-5L index score, the DLQI score, the NRS average itch and worst itch scores.

Additionally, a responder analysis will be conducted for DLQI where a responder is defined as the subject who achieved a post-baseline score of 0 or 1.

A responder analysis will also be conducted for NRS questionnaire where a responder is defined as a subject who has achieved a post-baseline itch score of < 4.

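### SAP Section 7 ties the responder 95% CI to an unstratified Fisher/chi-squared switch beside a stratified CMH p-value, Sections 7.2.1 and 7.4 ask for an adjusted CI, and no visible text names an interval

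*SAP*

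**What the plan says.** SAP Section 7 gives a general rule for responder analyses in two sentences. The first says the difference in proportions and its "two-sided 95% CI will be calculated using the Fisher's exact test or the Chi-squared test depending on the number of observations", with the switch defined only as "if cell counts are less than 5 then use Fisher's". The second takes the test of significance from a "Cochran Mantel-Haenszel (CMH) test adjusting for randomization stratification factors and the corresponding two-sided p-value will be presented". Adjustment for strata is mentioned only in the second sentence.

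The endpoint sections then differ:

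- **7.1.1, primary.** Each active arm is compared with placebo on the proportion "achieving PASI-75 at Week 12 between each active treatment and placebo using the CMH method as described in" Section 7.
- **7.2.1, active versus active PASI-75.** "the adjusted treatment difference, its associated 95% CI, and two-sided p-value will be presented for all 1:1 treatment comparison using the CMH method".
- **7.4, sPGA 0/1.** An adjusted difference is requested; "its associated 95% CI, and two-sided p-value will be presented for Week 4, 8 and 12 using the CMH method".
- **7.5.** "a responder analysis will be conducted for DLQI where a responder is defined as the subject who achieved a post-baseline score of 0 or 1", and similarly for the itch NRS. No comparison method is given.
- **PASI-50/90/100.** The visible SAP gives no comparison rule of their own.

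Protocol 10.3 stratifies efficacy analyses by prior biologic use and region unless otherwise noted. Protocol 10.3.2 says "Similar analyses as in the primary efficacy analyses will be performed to compare any two active arms" and asks for PASI-50/90/100 methods similar to those for PASI-75. SAP Section 5 commits to reporting p-values with two-sided 95% CIs.

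**The concern.** There are three gaps.

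1. **Two sources for the same quantity.** Section 7 bases the CI on tests of a single two-arm table, which carry no strata. Sections 7.2.1 and 7.4 want an adjusted difference and CI. On the most direct reading the primary PASI-75 interval falls under the Section 7 rule, because the CMH text that 7.1.1 points to yields only a p-value. An adjusted CI may have been intended.
2. **No interval is defined.** Fisher's exact and the chi-squared test are tests. Several different risk-difference intervals can reasonably be attached to each. The phrase CMH method in 7.2.1 and 7.4 does not name an interval either.
3. **The switch is ambiguous.** Observed and expected cell counts can send the same table to different branches.

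At stake is the reported interval and its agreement with the p-value beside it, mainly for weaker doses against placebo and for rarely met endpoints. Two programmers following the same sentence could report intervals that disagree about 0, and one of them could contradict the CMH p-value. No bias in the point estimate is claimed.

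**Working it through.** **Inputs.** From SAP Section 4: 35 per arm, PASI-75 60% versus 10%, two-sided alpha 0.05, power at least 99%. From SAP Section 3: 2 × 2 = 4 strata. The documents give no stratum sizes and no other response rates, so those used below are assumptions.

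**1. The plan's own figure.** Pooled normal approximation, mean rate 0.35:

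- critical difference = 1.96 × √(2 × 0.35 × 0.65 / 35) = 0.2235
- SE under the alternative = √((0.10 × 0.90 + 0.60 × 0.40) / 35) = 0.0971
- power = Φ((0.50 − 0.2235) / 0.0971) = Φ(2.85) = 99.8%

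Exact enumeration gives 99.8% for the chi-squared test and 99.5% for Fisher's. The stated power holds.

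**2. How often each branch applies at the planned rates.** With 10% on placebo, P(X ≤ 4 of 35) = 0.731. So the Fisher branch is used in 73% of comparisons if the rule means observed counts. If it means expected counts, the figure is about 0%.

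**3. One table, 10/35 versus 3/35** (difference 0.20).

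- Smallest observed cell is 3, giving the Fisher branch. Smallest expected cell is (10 + 3)/2 = 6.5, giving the chi-squared branch.
- One-stratum CMH: (10 − 6.5)² / [35 × 35 × 13 × 57 / (70² × 69)] = 12.25 / 2.685 = 4.56, p = 0.033. Fisher p = 0.062.
- Wald lower limit: 0.20 − 1.96 × √(0.2857 × 0.7143/35 + 0.0857 × 0.9143/35) = 0.20 − 1.96 × 0.0898 = +0.024.

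| Interval | Lower 95% limit |
|---|---|
| Exact unconditional, raw difference | −0.048 |
| Exact unconditional, score statistic | +0.010 |
| Wald | +0.024 |

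The exact one-sided p at zero difference is 0.060 for the raw difference and 0.019 for the score statistic, against a limit of 0.025. The first interval includes 0 and the second does not.

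**4. How often the reported CI contradicts the CMH p-value.** 40,000 simulated trials per scenario, 35 per arm, assumed strata of 11/7/10/7 per arm, no stratum effect, CMH without continuity correction, Wald in the chi-squared branch. Entries are the percentage of trials with CMH p < 0.05 and a CI that includes 0. The last column reads the Fisher branch as Fisher p ≥ 0.05.

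| Rates | Switch | Score exact | Raw exact | Fisher p |
|---|---|---|---|---|
| 60 v 10 (planned) | observed | 0.00 | 0.05 | 0.01 |
| 35 v 10 | observed | 0.1 | 16.9 | 6.4 |
| 30 v 10 | observed | 0.4 | 22.4 | 9.0 |
| 25 v 10 | observed | 0.7 | 22.6 | 9.9 |
| 15 v 2 | observed | 3.6 | 49.3 | 26.7 |
| 30 v 10 | expected | 0.4 | 2.5 | 1.2 |
| 15 v 2 | expected | 3.6 | 46.3 | 25.8 |

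The reverse conflict (CMH p ≥ 0.05, CI excludes 0) is 0.8–1.5% at 25–35% versus 10%, 0.0% at 15% versus 2% and 0.03% at the planned rates. With Wald throughout, the conflict in the table falls to 0.15% at 30% versus 10% and 0.00% at 15% versus 2%. Changing the strata to 5/5/15/10, adding stratum effects of ±0.5 logit, or both, gives (observed switch) 0.5–0.6% score and 16.9–22.6% raw at 30% versus 10%, and 4.0–5.4% and 49.4–53.3% at 15% versus 2%.

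**5. How often the two exact readings disagree about 0.** Exact enumeration, no strata needed:

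| Rates | Observed switch | Expected switch |
|---|---|---|
| 60 v 10 | 0.05% | 0.0% |
| 30 v 10 | 22.1% | 2.2% |
| 15 v 2 | 45.6% | 42.5% |

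**6. Whether a matched interval removes the conflict.** The stratified Miettinen-Nurminen statistic at zero difference, with Mantel-Haenszel weights and the N/(N−1) factor, is algebraically the CMH statistic without continuity correction. In the simulations there were 0 mismatches in 40,000 trials in each of five scenarios.

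**The case against.** The strongest case against has five parts.

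- **The conflict is not caused by stratification.** With no strata at all, the 30% versus 10% figures are 0.4% (score), 22.5% (raw) and 9.05% (Fisher), almost the same as with four strata. This stands: the unnamed interval drives the conflict, more than the mismatch between a stratified p-value and an unstratified CI.
- **The large percentages rest on the raw-difference exact interval, which the SAP never mentions, and on rates it does not assume.** This also stands. They bound what the wording permits and are not a forecast. At the documented 60% versus 10% the conflict is about 0.1% or less, and at 21/35 versus 4/35 every interval excludes 0 (lower limit 0.25 raw, 0.26 score, 0.29 Wald).
- **Section 7 is worded as a default, so 7.2.1 and 7.4 could simply override it.** That is a fair reading. It still leaves the primary PASI-75 interval on the Section 7 rule as written, and the adjusted interval unnamed elsewhere.
- **Applying the rule to PASI-50/90/100 and to the DLQI and NRS responders is inference.** That is true, but no other visible rule is available for them.
- **Redacted text in Section 7 might name an interval.** It might. It would not remove the difference between the visible Section 7 sentence and Sections 7.2.1 and 7.4.

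**Conclusion.** The concern holds on the visible text. The SAP gives two different bases for responder intervals, leaves the branch rule undefined and names no interval. The effect on the planned primary result is negligible. For weaker arms or rare responder endpoints, the choice left open can decide whether the reported CI includes 0: at an assumed 30% versus 10%, two admissible readings differ in 22.1% of trials on observed counts and 2.2% on expected counts. At an assumed 15% versus 2% they differ in more than 40% either way. For 7.2.1 and 7.4 the point is narrower: the interval is unnamed. The conflict rates with the CMH p-value depend on the assumed rates, strata and intervals. The CMH test, alpha, power and sample size are unaffected. This should be corrected, but it does not threaten the trial's main conclusion.

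**What to change.** Replace the Fisher/chi-squared sentence in SAP Section 7 with one rule for every responder endpoint (7.1.1 including PASI-50/90/100, 7.2.1, 7.4 and the responder analyses in 7.5). Suggested wording:

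> The treatment difference will be the Mantel-Haenszel-weighted risk difference over the randomisation strata, with a [named] stratified two-sided 95% CI, reported beside the CMH p-value from the same strata.

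A stratified Miettinen-Nurminen score interval with Mantel-Haenszel weights is a suitable choice, because it agrees with the uncorrected CMH test about zero difference. Stratified Newcombe is acceptable, with some residual disagreement. Label any unadjusted interval as supportive and name its method. This removes the need for a cell-count switch.

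The cost is SAP wording and minor programming, with no extra patients or data.

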6.12.2. Prohibited Medications

Medication and treatment restrictions applicable before the dosing period are listed as exclusion criteria in [Section 5.3](#). These restrictions are applicable for the duration of the study and are summarized in [Table 2](#). Prior and concomitant medication will be recorded.

Table 2 Prohibited Treatments

Treatment Category	Examples ^A	Washout Period ^B
Topical medications or treatments that could affect psoriasis evaluation	corticosteroids, anthralin, calcipotriene, vitamin D derivatives, retinoids	2 weeks
Phototherapy or systemic medications or treatments that could affect psoriasis evaluation	oral or injectable corticosteroids, retinoids, 1,25-dihydroxy vitamin D3	4 weeks
Therapeutic agents targeted to IL-12 or IL-23	ustekinumab, guselkumab, tildrakizumab, risankizumab	6 months
Therapeutic agents targeted to IL-17	secukinumab, ixekizumab, brodalumab	4 months
TNF α inhibitors	etanercept, infliximab, adalimumab	2 months
Systemic immunosuppressants or immunomodulatory drugs	corticosteroids (oral/IV/IM/SC), methotrexate, azathioprine, cyclosporine, mycophenolate mofetil	4 weeks or 5 half-lives ^C
Agents that modulate B cells	rituximab, ocrelizumab	6 months
Agents that modulate T cells	abatacept, alemtuzumab	3 months
JAK inhibitors or TYK2 inhibitors	baricitinib, tofacitinib, upadacitinib, ruxolitinib, fedratinib, deucravacitinib	4 weeks
Investigational agents		30 days or 5 half-lives ^C
Proton pump inhibitors	omeperazole, esomeprazole, pantoprazole	Prior to Study Day 1

- A. Including but not limited to
- B. Prior to randomization on Study Day 1
- C. Whichever is longer

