7.2. Study Drug Discontinuation

Patients should discontinue study drug for any of the following reasons:

- Malignancy, not including local and non-serious basal, squamous cell skin cancer or ductal carcinoma in situ
- Pregnancy
- Anaphylaxis, anaphylactoid or serious hypersensitivity reaction
- Use of any medication, intended to chronically treat psoriasis (refer to [Section 6.12.2](#)), other than those documented at screening
- Adverse event which in the opinion of the investigator or SMC precludes the patient from safely continuing in the study
- Patient is noncompliant with study requirements

The date and reason for discontinuation should be documented in the eCRF.

Patients who discontinue study drug should continue in the study to complete all scheduled assessments.

Those patients who are unwilling or unable to complete all remaining study assessments should return to the study site 2 weeks (\pm 7 days) after the date study drug was discontinued, to complete the early study termination assessments (ET Visit).

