5.1 Analysis Populations

The following analysis populations are defined in this study:

- Modified Intent-to-Treat (mITT) Population: All randomized subjects who received at least one dose of study drug, with analyses conducted according to the assigned treatment. This will be the analysis population used for the primary efficacy analysis at Week 12.
- Intent-to-treat (ITT) Population: All randomized subjects, regardless of whether they receive study drug, with analyses conducted according to the assigned treatment.
- Per-protocol (PP) Population: All subjects in the ITT population who have received at least one dose of study drug as assigned, have both baseline and at least one post-baseline PASI score, and have no important protocol deviations (IPD) which may affect key primary and secondary efficacy endpoints in the treatment period.
- Safety Analysis Population: All randomized subjects who receive at least one dose of study drug with analyses conducted by actual treatment received.
- PK Analysis Population: All randomized subjects who receive at least 1 dose of ESK-001 and have at least one non-missing PK concentration with analysis conducted by actual treatment received.

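### In the readable SAP, non-responder imputation is tied to leaving the study, so a Week 12 response reached on another psoriasis treatment counts for the randomized arm

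*SAP*

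**What the plan says.** **Imputation rule.** SAP Section 7 states that "subjects who drop out of the study before Week 12 will be considered as a non-responder at the week 12 visit", and then: "No imputation will be applied at any other post-baseline visits". SAP 5.3 otherwise imputes nothing unless the SAP says so, and points to Section 7 for responder analyses. A redacted block follows the rule directly, and four more close the opening text of Section 7.

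**Stopping study drug.** Protocol 7.2 lists among the reasons for stopping study drug: "Use of any medication, intended to chronically treat psoriasis". It refers to Section 6.12.2 and exempts medication documented at screening. Of the Section 6.12.2 restrictions the protocol says: "These restrictions are applicable for the duration of the study".

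**Follow-up afterwards.** Protocol 7.2 continues: "Patients who discontinue study drug should continue in the study to complete all scheduled assessments". There is an exception: "Those patients who are unwilling or unable to complete all remaining study assessments should return to the study site 2 weeks" for an early termination visit.

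**Analysis set.** The primary efficacy set is mITT: "All randomized subjects who received at least one dose of study drug, with analyses conducted according to the assigned treatment". As a check, the SAP offers: "A sensitivity analysis using the ITT or PP analysis set may be performed as appropriate".

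**The concern.** The primary objective is PASI-75 on ESK-001 doses against placebo after 12 weeks of treatment. The readable rule counts a patient who leaves the study as a failure. It sets no such rule for a patient who stops study drug, starts another psoriasis treatment and stays. If that patient clears on the other treatment by Week 12, the response counts for the randomized arm.

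One placebo arm serves all five primary comparisons, so a credited response there moves all five differences. A credited response in an active arm moves that arm's comparison with placebo and its comparisons with the other doses. The size of effect at each dose is what a dose-ranging study has to estimate, so responses that belong to another drug matter even where significance is secure.

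**Working it through.** **1. Does the rule reach these patients?**

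| Step | Source | Result |
|---|---|---|
| Patient starts chronic psoriasis medication | Protocol 7.2 | Study drug stops |
| Patient stays for all assessments | Protocol 7.2 | Not a dropout |
| PASI, BSA and sPGA assessed at Week 12 | Protocol 1.3 | Week 12 value normally exists |
| Non-response imputed for dropouts | SAP 7 | Not triggered |
| Analysis by assigned treatment | SAP 5.1 | Response credited to that arm |

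Patients who will not or cannot continue go to the early termination visit and leave the study. The rule does cover them.

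**2. The plan's own power.** Inputs from SAP Section 4 and Protocol 10.7: 35 per arm, two-sided 0.05, 10% versus 60%. The normal approximation with pooled variance under the null gives 99.78%, and exact enumeration of Fisher's test gives 99.51%. Both agree with the stated minimum of 99%.

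**3. Effect of k switched placebo responders.** Fix k of the 35 placebo patients as responders on other treatment and let the other 35 − k respond at 10%. The placebo count is then k + Bin(35 − k, 0.10), with expected rate (k + 0.10(35 − k))/35:

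- k = 1: 4.4/35 = 12.6%
- k = 2: 5.3/35 = 15.1%
- k = 3: 6.2/35 = 17.7%

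Each such patient adds 0.9/35 = 2.6 points to the expected placebo rate. Classing the same patient as a responder rather than a non-responder moves the observed rate by 1/35 = 2.9 points.

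Power is the sum of the probabilities of all tables with |z| > 1.96, where z = (difference in proportions)/√(p̄(1 − p̄) × 2/35) and p̄ is the pooled proportion:

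| k | 60% vs 10% (planned) | 40% vs 10% (assumed) |
|---|---|---|
| 0 | 99.8% | 85.2% |
| 1 | 99.5% | 76.8% |
| 2 | 99.0% | 66.4% |
| 3 | 98.0% | 54.7% |

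This is the unstratified two-sample test used for the sample size. The planned CMH test will differ slightly.

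**4. Direction.** Let s be the share of an arm that switches and stays, p the rate in the others, and q the Week 12 PASI-75 rate after switching.

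- Credited rate: (1 − s)p + sq
- Rate with switchers as non-responders: (1 − s)p
- Difference when credited, minus difference under non-response: q(s_active − s_placebo)

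The documents give neither s nor q, so these are illustrations at 60% versus 10% (power by the normal approximation):

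| Switching share, q | Credited | Non-response | Gap |
|---|---|---|---|
| 20% placebo, 5% active, q = 80% | 61.0% − 24.0% = 37.0 points, power 89.7% | 57.0% − 8.0% = 49.0 points, power 99.8% | 0.80 × (−0.15) = −12 points |
| 5% placebo, 20% active, q = 80% | 64.0% − 13.5% = 50.5 points, power 99.7% | 48.0% − 9.5% = 38.5 points, power 96.1% | 0.80 × (+0.15) = +12 points |
| Equal shares | same difference | same difference | 0 |

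**The case against.** **The redaction.** A reader might infer that dropout is the only trigger in the plan. The documents do not support that. Blacked-out text sits directly after the rule, where a provision on other psoriasis treatment would naturally go. This stands: the point is limited to the readable text and the fix is conditional.

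**Treatment policy is legitimate.** Protocol 10.3 adopts an intent-to-treat approach, and follow-up after stopping drug fits a strategy that counts outcomes as observed. This stands in part. Such a choice is defensible, but no readable text names it, and it sits uneasily with failing every dropout and with an objective framed around 12 weeks of treatment. The optional sensitivity analyses do not settle it. ITT counts the switcher in the same way. PP removes the patient instead of counting a failure, and only if the event is judged an important deviation affecting key endpoints.

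**Direction and frequency.** A reader might infer that switching is commonest on placebo and so biases against the drug. The documents give no rate by arm. Treatment is blinded and lasts 12 weeks, and open-label ESK-001 is offered after Week 16, which gives some reason not to switch. This stands.

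**Size.** The 40% arm is not a plan figure, and at the planned effect three such patients cost under 2 points of power. This also stands. A reader might infer that the stated power is wrong or the trial underpowered, but the stated figure reproduces.

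**Scope of the remedy.** Table 2 reaches well beyond psoriasis treatment, to proton pump inhibitors for example. Failing a patient for any Table 2 item would be too broad. The fix is narrower for that reason.

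**Conclusion.** The point holds for the readable text. A Week 12 PASI-75 or sPGA 0/1 response reached on a chronic psoriasis medication, after study drug has stopped, counts for the randomized arm, and no firm sensitivity analysis shows how much this matters.

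The effect on the planned 60% versus 10% comparison is small: 99.8% falls to about 98% with three switched placebo responders. It is larger for a weaker dose: for an assumed 40% versus 10%, 85% falls to about 77%, 66% and 55% with one, two and three. The number of switchers is an assumption throughout. The sign depends on which arm switches more, and equal switching with the same q leaves the difference the same under either rule. The conclusion lapses if the redacted text already sets a rule for these patients.

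**What to change.** First check the redacted text after the imputation rule. If it already covers these patients, nothing is needed. Otherwise, amend SAP Section 7 before unblinding:

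1. Also count as a Week 12 non-responder any subject who, before the Week 12 assessment, starts a medication or phototherapy intended to treat psoriasis that meets the Protocol 7.2 discontinuation reason. Keep the exemption for medication documented at screening, and limit the rule to psoriasis treatments instead of all of Table 2.
2. Flag these subjects from concomitant-medication data before unblinding. Confirm where on-study phototherapy is recorded, since SAP 6.4 also refers to concomitant procedures.
3. Leave the rule against imputation at other visits unchanged, or amend it explicitly. The Week 4 and Week 8 comparisons depend on which is chosen.
4. Pre-specify the as-observed (treatment-policy) result as a sensitivity analysis.

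The cost is a few SAP sentences, one derived flag and one extra table, with no change to patient management or data collection. The downside is small: a genuine responder to study drug who used such a product counts as a failure, and the sensitivity analysis shows how much that matters.
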